6.2.1. Fresh Biopsy Patient AE

Summary of adverse events, not necessarily TEAEs, experienced within 7 days of fresh biopsy will be generated by SOC, PT, and CTCAE grade. A listing of AEs experienced within 7 days of biopsy will also be generated for patients who have undergone fresh biopsy.

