Procedure	Pre-screening	Screening	Cycle 1 C=3 weeks		C2+	C3	EOT	30-Day Follow-up	Survival Follow-up
			D1	D8	D1	D8	≤ 7d from discon.	30 (+14) days from last dose	Every 3 months (±1 month) from EOT
Blood sample for Biomarkers	•	•							
Pregnancy Test ⁱ		• ⁱ	• ^f		•			•	
Ophthalmic Exam ^j		• ^c	Every other cycle from time treatment-emergent eye disorder first reported				• ^j	• ^j	
Ocular Symptom Assessment ^k		• ^c	•		•		•	•	
Radiologic Tumor Assessment ^l		• ^a	Every 6 (±1) weeks from C1D1 for first 36 weeks, then every 12 (±3) weeks				• ^m	• ^m	
CA-125 ⁿ		• ^c	Collect at each radiologic tumor assessment (± 4 days)				• ^m	• ^m	
MIRV administration			•		•				
Record AE/SAEs and concomitant medications	• ^o	•	Collected continuously while patients are on study						
Blood sample for PK ^p			•	•	• ^p	•	•	• ^p	
Blood samples for immunogenicity ^q			•		•		•	•	
Survival Phone screen, including new anticancer therapy ^r									•

Abbreviations: AE = adverse event; aPTT = activated partial thromboplastin time; C = cycle; CA = cancer antigen; D = day; ECOG = Eastern Cooperative Oncology Group; ECG = electrocardiogram; EOT = End of Treatment; FFPE = formalin-fixed-paraffin-embedded; INR = international normalized ratio; PK = pharmacokinetics; PT = prothrombin time; SAE = serious adverse event.

Note: A patient's *BRCA* mutational status (germline or somatic mutation in tumor tissue) will be collected as part of her medical history if available. Patients without a known mutation will be classified as unknown.

- ^a Must be within 28 days before C1D1 unless otherwise specified.
- ^b ECG assessment may be performed predose at C1D1 if not performed previously up to 28 days prior to first dose of MIRV.
- ^c Must be within 14 days before C1D1.
- ^d Testing for FR α expression is required for all patients. Those who do not have archival tumor tissue to submit will be required to undergo procedures to obtain a new biopsy using a low-risk, medically routine procedure during the Pre-screening period to confirm eligibility. If the archival tumor tissue does not meet FR α criteria, a new biopsy tumor sample may be submitted and used to confirm this criterion.
- ^e Complete physical examination (PE) is required at Screening and the 30-Day Follow-up visit. At all other study visits while on MIRV, patients will have symptom-directed PEs.

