- ^m If a patient discontinues before documentation of PD, a tumor assessment and CA-125 will be assessed at the EOT or 30-Day Follow-up visit, if not performed within the previous 6 weeks. Tumor assessments and CA-125 will continue to be performed every 12 (\pm 3) weeks until PD is documented per RECIST 1.1 or the patient starts new anticancer therapy. Patients who discontinue MIRV for reasons other than progressive disease (PD) will continue with tumor assessments until documentation of PD or the start of a new anticancer therapy, whichever comes first. Prior to Week 36 (from Cycle 1, Day 1), assessments should occur every 6 weeks (\pm 1 week) as allowed by local requirements but must occur at an interval of no more than 12 weeks. After Week 36, assessment will occur every 12 weeks (\pm 3 weeks) until documentation of PD, death, the start of new anticancer therapy, or patient's withdrawal of consent (whichever occurs first).

- ⁿ CA-125 will be measured at the time of every tumor assessment (± 4 days) (responses will be confirmed according to GCIG criteria [Appendix C](#)).
- ^o Only AEs/SAEs which are considered related to a study procedure (ie blood draw or fresh tumor biopsy) will be captured during the Pre-screening period, ie from the time of signing the Pre-screening consent (if one is utilized) until the signing of the main study informed consent, or until the patient is determined to be a screen failure.
- ^p Blood samples for PK analysis will be taken within 1 hour after MIRV infusion on Day 1 of Cycles 1 and 3, and on Day 8 (± 24 hours) of Cycles 1 and 3. Samples will also be collected prior to dosing on Day 1 of Cycles 2 and 4, and EOT and also at the 30-Day Follow-up, if feasible.
- ^q Immunogenicity will be assessed in PK samples collected prior to dosing (predose) on C1D1, C2D1, C4D1, at EOT, and 30-Day Follow-up.
- ^r Survival follow-up assessments will occur every 3 months (± 1 month) until death, the patient is lost to follow-up or withdrawal of consent for survival follow-up, or EOS (whichever comes first). These assessments may be conducted by telephone. Information on the start of new anticancer therapy (including start date, therapy type/name, and response on treatment) should be collected. Additional survival follow-up calls may occur periodically if needed for regulatory requests or at time of database lock for either primary or final analysis.

TABLE OF CONTENTS

SPONSOR SIGNATURE PAGE	2
SPONSOR CONTACT LIST	3

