8. ASSESSMENT OF SAFETY

8.1. Recording Adverse Events and Serious Adverse Events

Adverse Events (AEs), including those attributed to study procedures, will be documented in the clinical trial database and monitored continuously throughout the study from the time of informed consent until 30 days after the patient's last study treatment.

Only AEs/SAEs which are considered related to a study procedure (ie blood draw or fresh tumor biopsy) will be captured during the pre-screening period, ie from the time of signing of the pre-screening informed consent (if one is utilized) until the time of signing of the main study informed consent, or until the patient is determined to be a screen failure. All AEs and SAEs, regardless of causality, will be captured after the main study ICF has been signed.

SAEs will continue to be followed by ImmunoGen Pharmacovigilance until resolution, stabilization or return to baseline. Beyond this defined reporting period, any unsolicited SAE assessed as related to the study drug by the Investigator and reported to ImmunoGen will be collected and processed. Additional information obtained after database lock, will reside solely in the safety database.

The Investigator should follow and provide updates for all AEs until clinical recovery is complete, laboratory values return to normal, the patient stabilizes, or death occurs, to ensure the safety of the patients. This may mean that observations continue beyond the last planned visit per protocol and that additional investigations may be requested by the Sponsor.

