A model of the pre-screening and the main study ICF will be provided to the sites separately for this protocol. The main study consent can be used to confirm a patient's consent to all study procedures and all study-specific screening tests. The pre-screening ICF can be used to pre-screen patients for FR α status before performing any additional study related tests. If a patient is eligible based on FR α expression level, the patient will be provided the main study consent and only after signing the main study ICF will additional study-specific screening tests be performed. Alternatively, the patient can be consented on both pre-screening and main study ICF at the same time; and FR α testing and study-specific screening assessments can be carried out in parallel.

Patients must be consented to the most current version of the ICF during their participation in the study.

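### The 7-day fresh-biopsy adverse-event table (SAP 6.2.1) mixes two event-capture rules, so its frequencies depend on the consent route as well as on the biopsy

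*SAP*

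**What the plan says.** SAP 6.2.1 asks for one summary: "Summary of adverse events, not necessarily TEAEs, experienced within 7 days of fresh biopsy will be generated by SOC, PT, and CTCAE grade". It adds a listing of the same events for patients who had a fresh biopsy. It sets no condition on causality, makes no distinction by consent and names no denominator.

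The protocol fixes which events reach the database in that window:

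- **Timing of the biopsy.** Table 2, footnote d, says that patients without archival tissue must have "a new biopsy using a low-risk, medically routine procedure during the Pre-screening period to confirm eligibility". A new sample may also be submitted if the archival tissue fails the FRα criterion.
- **Restricted capture.** Protocol 8.1: "Only AEs/SAEs which are considered related to a study procedure (ie blood draw or fresh tumor biopsy) will be captured during the pre-screening period". Table 2, footnote o, gives the period as running "from the time of signing the Pre-screening consent (if one is utilized) until the signing of the main study informed consent", or until screen failure. Sections 8.1.1.1 and 8.2.1 repeat the rule.
- **Full capture.** Protocol 8.1: "All AEs and SAEs, regardless of causality, will be captured after the main study ICF has been signed".
- **Choice of consent route.** Protocol 7.1 lets sites merge the two forms. Section 12.1.1 ties the pre-screening form to sites that ask to pre-screen. Section 12.1.2 allows the main consent to cover all screening tests, and says that "the patient can be consented on both pre-screening and main study ICF at the same time".

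**The concern.** A fixed-window table of all recorded events is easy to interpret only if the same events are recorded for everyone in it. Here they are not. A headache judged unrelated, three days after the biopsy, is counted for a patient who has already signed the main form. It is never recorded for a patient who has signed only the pre-screening form. The second patient adds procedure-related events to the table, and the first adds events of any cause.

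The pooled result is then neither the biopsy-related frequency nor the all-cause frequency. It moves with the consent mix even when biopsy risk is constant. SAP 6.2.1 is the only summary table the SAP plans for events around this biopsy, a procedure done for study eligibility, so the table should have a clear meaning.

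**Working it through.** The documents state no biopsy event rate, so there is no planned figure to reproduce. The check is a comparison of the capture rules, followed by an illustration.

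**Step 1. Capture within the 7 days, by consent route**

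| Route | Related to a study procedure | Unrelated |
|---|---|---|
| Separate pre-screening consent, main form not yet signed | recorded | not recorded |
| Separate pre-screening consent, main form signed within the 7 days | recorded | recorded from signing only |
| Merged, simultaneous or earlier main consent | recorded | recorded |

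SAP 6.2.1 adds the three rows together. SAP 6.2 says that events attributed to study procedures before the first dose go on the AE form. It does not repeat the pre-screening restriction or adjust for it.

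**Step 2. Formula**

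Let r be the 7-day risk of a biopsy-related event, b the 7-day risk of an unrelated event, and q the share of biopsied patients with all-event capture throughout. Assume that the two kinds of event are independent and that the other patients stay under restricted capture for all 7 days. Then

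recorded rate = r + q(1 − r)b.

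**Step 3. Numbers**

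All inputs are assumptions: r = 5%, b = 10 to 30%, q from 0 to 1. For example, with q = 0.1 and b = 10%: 0.05 + 0.1 × 0.95 × 0.10 = 5.95%.

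| b | q = 0 | q = 0.1 | q = 0.5 | q = 1 |
|---|---|---|---|---|
| 10% | 5.0% | 5.95% | 9.75% | 14.5% |
| 20% | 5.0% | 6.9% | 14.5% | 24.0% |
| 30% | 5.0% | 7.85% | 19.25% | 33.5% |

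From q = 0 to q = 1 the rate rises by (1 − r)b. With r from 0 to 20% and b from 10 to 30%, that is 0.80 × 0.10 = 8 points up to 1.00 × 0.30 = 30 points, with no change in biopsy risk.

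**Step 4. Main consent signed inside the window**

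Suppose separate-consent patients sign the main form with 3 of the 7 days left, and unrelated events arise at a constant rate. Their unrelated risk under full capture is 1 − (1 − b)^(3/7). At b = 20% this is 9.1%, so their recorded rate is 0.05 + 0.95 × 0.091 = 13.7%, against 24.0% with full capture. The gap narrows but remains.

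**Step 5. Effect of the filter**

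If only procedure-related events are counted, the term in q disappears and the rate is r for any consent mix.

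**The case against.** The strongest reply is that biopsy harm is captured for every patient. Procedure-related events are recorded under both routes, so the table does respond to biopsy risk and only the added background varies. This stands. A reader might infer that the table measures the consent form and not the biopsy. The documents do not support that, because at every q the recorded rate rises with r.

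A reader might also see a contrast purely between sites. That fails too: Protocol 12.1.2 allows simultaneous signing patient by patient, and a separate-consent patient moves to full capture on signing the main form.

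On size, an even consent mix would give about 10 to 19% in the illustration, but nothing in the documents supports an even mix. Protocol 7.1 presents the separate form as the usual course and merging as the exception, which points to a smaller q, though no proportion is stated.

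The listings in SAP 6.2 and 6.2.1 also show these events, and the breakdown by SOC, PT and grade helps a reader to judge them. The table is therefore not the only view of biopsy harm. But listings cannot supply unrelated events that were never recorded, and they do not put the summary on one footing.

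Finally, SAP 6.2.1 does not claim to estimate a biopsy-related rate, and an all-cause count avoids reliance on attribution. That would be a fair defence if all-cause events were collected for everyone. Under separate consent they are not: attribution already decides what is recorded.

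**Conclusion.** The concern holds in limited form. Two capture rules operate in the same 7-day window, SAP 6.2.1 combines them, and no other part of the SAP separates them. The tabulated frequencies depend on the consent route as well as on the biopsy.

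The size cannot be determined from the documents. Under the assumed 5% related and 10 to 30% unrelated risks, the distortion runs from nothing (no all-event capture), through about 1 to 3 percentage points (10% of patients with it), to 9.5 to 28.5 points (all patients with it). These figures assume independent events and, for separate-consent patients, no main consent within the 7 days.

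The consequence is small. This is one descriptive table with no test or threshold attached, for a subset of patients of unstated number. ORR, DOR and the TEAE tables are not affected. It is worth correcting because correction is cheap.

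**What to change.** In SAP 6.2.1:

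1. Make the main table the events within 7 days of fresh biopsy that are attributed to the biopsy procedure. Both consent routes collect these. The capture rule in Protocol 8.1 already requires that judgement, but the only causality scale shown (Protocol 8.1.2, Table 11) is for study medication. The sponsor should confirm that attribution to the procedure is a recorded field.
2. Show all-cause events in a second table, only for patients whose main consent was signed on or before the biopsy date, with that number as the denominator.
3. If no procedure-attribution field exists, keep the existing table but split it by whether the main consent had been signed by the biopsy date.

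SAP 4.1.1 lists an informed consent date without saying which form it refers to. The date of the main consent is the one needed.

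The cost is SAP wording, a filter on attribution and consent date, and one small extra table. SAP 1.1 allows changes before final database lock. The downside is that the main table then rests on investigator attribution.

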6.2.2. Infusion-related Reactions

Both broad and narrow standard MedDRA query (SMQ) for hypersensitivity will be performed. A summary table of all TEAEs matching broad or narrow SMQ will be generated by SOC, PT, and CTCAE grade. A listing will also be generated.

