5.5.5. Potential Infusion-related Reactions

Some patients treated with IV infusions of therapeutic drugs have experienced concurrent infusion-related reactions (IRR) (see CTCAE Version 5.0). The signs and symptoms may vary and include for example, headache, fever, facial flushing, pruritus, myalgia, nausea, chest tightness, dyspnea, vomiting, erythema, abdominal discomfort, diaphoresis, shivers, lightheadedness, hypotension, palpitations, and somnolence. Anaphylaxis might occur at any time during an infusion. Before any infusion is started, appropriate medical personnel, medication (eg, epinephrine, inhaled beta agonists, antihistamines, and corticosteroids), and other required resources to treat anaphylaxis must be readily available. In general, Investigators should manage acute allergic or hypersensitivity reactions according to Institutional practices. General guidelines for the management of acute IRRs and for subsequent retreatment are provided in [Table 7](#). Delayed IRRs may occur; therefore, patients should be advised to seek immediate medical treatment if symptoms newly develop and/or recur after discharge from clinic.

Patients who experience \geq Grade 2 IRR during or immediately after administration of MIRV will have blood drawn for determination of drug concentration and ADAs to MIRV. The sample should be obtained within three hours of the onset of the reaction and one week later. Such patients should undergo all scheduled efficacy and safety evaluations.

Table 7: Management Guidelines for Potential Infusion-Related Reactions

Infusion Reaction CTCAE v5.0 Severity Grade	Management
Grade 1: Mild, transient reaction	
 • Maintain infusion rate unless progression of symptoms to \geq Grade 2; if symptoms worsen, refer to guidelines below. • Promethazine (or equivalent) 150 mg PO per day (Q4h) PRN for nausea • Diphenhydramine (or equivalent) 25-50 mg PO or IV PRN • Methylprednisolone (or equivalent) 125 mg IV PRN

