6. PHARMACOKINETIC, IMMUNOGENICITY, AND BIOMARKER ASSESSMENTS

6.1. Pharmacokinetic Assessments – Mirvetuximab Soravtansine

The PK properties of MIRV and key metabolites will be evaluated following IV administration, as outlined in [Table 2](#) and [Table 8](#). Plasma samples will be collected to determine the concentration of MIRV (conjugate, total Ab, free DM4, S-methyl DM4 and possibly other metabolites).

Blood samples for PK analysis will be taken at the following timepoints:

Table 8: Pharmacokinetics Sampling Time Points

Visit	Time Point
C1D1	Predose (immunogenicity only); ≤ 1 hour after MIRV infusion
C1D8	Anytime during visit
C2D1	Before dosing
C3D1	≤ 1 hour after MIRV infusion
C3D8	Anytime during visit
C4D1	Before dosing
EOT	Anytime during visit
30-Day Follow-up	Anytime during visit

Abbreviations: C = cycle; D = day; EOT = End of Treatment.

Unscheduled visit: Any patient who experiences a ≥ Grade 2 IRR during or within 3 hours after the administration of MIRV will have blood drawn within 3 hours of the onset of the reaction and one week later for determination of drug concentration and ADAs to MIRV.

PK samples may also be obtained as feasible at any time during the treatment period for assessment of treatment-related SAEs if deemed appropriate by the Investigator and Sponsor.

Procedures for collection, storage and shipment of samples are provided in the applicable Laboratory Manual.

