6.2. AEs

AEs will be documented on the AE CRF and monitored continuously throughout the study from the time of informed consent until 30 days after the patient's last MIRV or until the event has resolved, stabilized, or returned to baseline. AEs attributed to study procedures, including those events that occur prior to the first dose, should also be documented on the AE CRF.

AE data are available to ImmunoGen from 2 sources, the clinical database and the serious adverse event (SAE) forms. While reconciliation will be performed, the production of data summaries and listings will be based on the data collected on the clinical database.

Pre-treatment AEs are defined as AEs with an onset date prior to the first dose of MIRV. TEAEs are defined as AEs with an onset date on or after the first dose of MIRV, and within 30 days of the last dose of MIRV or prior to the start of a new anti-cancer treatment, whichever occurs first. Medical history conditions that exist before the initiation of MIRV but worsen in severity during the study will also be recorded on the AE CRF as an AE and will be included as treatment-emergent in the summary tables and listings.

The adverse events will be coded using MedDRA (Version 24.0), associating lower-level terms with PT and SOC by the primary hierarchy. The tables will display the counts and percentages of patients who reported at least 1 TEAE in each SOC represented in the AE data. Within each SOC, the tables will display the counts and percentages of patients reporting at least 1 TEAE as designated by the PT.

AEs are graded using CTCAE Version 5.0. AE summaries may include summaries for all AEs and by the maximum CTCAE grade for the item being summarized (ie, SOC or PT). In these cases, the outputs will include a row for All Grades as well as rows for the 5 potential CTCAE grades, Grade 1 (Mild), Grade 2 (Moderate), Grade 3 (Severe), Grade 4 (Life threatening or disabling), or Grade 5 (Death). AEs missing a severity grade will not be included in the Grade 1-5 rows of the tables. An AE reported by a patient more than once will be represented in the most severe category. TEAEs will be categorized as MIRV-related if "Possibly Related", "Probably

Related", or "Definitely Related" is selected by investigator. AEs missing relationship to MIRV will be included in the Related TEAE tables and listings.

The following summary tables will be produced:

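### The SAP's infusion-related-reaction table is a hypersensitivity term search with no link to an infusion and no use of investigator-identified reactions

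*SAP*

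**What the plan says.** SAP 6.2.2 carries the heading Infusion-related Reactions and begins: "Both broad and narrow standard MedDRA query (SMQ) for hypersensitivity will be performed". It continues: "A summary table of all TEAEs matching broad or narrow SMQ will be generated by SOC, PT, and CTCAE grade". A listing is added. The section sets no onset window, relatedness condition or requirement that the investigator called the event an infusion reaction.

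The time limit comes from the TEAE definition in SAP 6.2: "an onset date on or after the first dose of MIRV, and within 30 days of the last dose of MIRV", or before new anticancer treatment if that starts sooner.

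Protocol 5.5.5 introduces the concept by saying that some patients given IV drugs "have experienced concurrent infusion-related reactions (IRR) (see CTCAE Version 5.0"). Its Table 7 sets management by grade. Two sentences in the protocol give timing, both for Grade 2 or higher events and both about extra blood sampling. Section 5.5.5 has "IRR during or immediately after administration of MIRV will have blood drawn"; Section 6.1 has "IRR during or within 3 hours after the administration of MIRV will have blood drawn". Section 5.5.5 also states: "Delayed IRRs may occur; therefore, patients should be advised to seek immediate medical treatment". It gives no upper time limit for delayed reactions.

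Protocol 10.3 names no infusion-reaction analysis, and neither document defines an infusion-reaction rate.

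**The concern.** A table headed infusion-related reactions and split by CTCAE grade will be read as the incidence and severity of reactions to the infusion, and set against the grade-based rules in Protocol Table 7. The events in it are chosen differently. A matching event on Day 15 of a cycle counts the same as one that starts while the drug is running. In the other direction, a reaction that the investigator diagnosed but that was recorded under a term outside the query does not appear at all.

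No other planned summary fills the gap. SAP 6.2 gives time to first onset only for its focused groups (ocular, peripheral neuropathy, pneumonitis). The SAP does tie events to a procedure where it means to: Section 6.2.1, immediately before, limits biopsy-related events to 7 days.

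What is at stake is the reading of one descriptive safety table.

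**Working it through.** The documents state no infusion-reaction rate, so there is no plan figure to reproduce. The check compares the texts and then illustrates the scale.

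**Comparison of texts**

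| Feature | SAP 6.2 and 6.2.2 | Protocol 5.5.5 and 6.1 |
|---|---|---|
| Which events | Hypersensitivity query, broad or narrow | Reactions to infusion, with an open list of signs that includes headache, nausea and myalgia |
| Timing | Whole TEAE window | Concurrent with infusion; delayed reactions possible, no upper limit |
| Investigator diagnosis | Not used | Implied by management by grade |

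The two selections overlap, but neither contains the other. The query's term list is not in the documents, so it cannot be checked how many of the protocol's non-specific signs it would catch.

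**Share of a cycle near an infusion** (one infusion per 21 days, Protocol 4.1.2)

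- 3 hours: 3 / (21 × 24) = 3/504 = 0.6%
- 24 hours: 24/504 = 4.8%
- Infusion date plus next calendar day: 2/21 = 9.5%

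If unrelated matching events start evenly over the cycle (an assumption), 1 − 0.095 = 0.905, or about 90%, start outside the two-day window. The planned table includes all of them, inside and outside.

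**What unrelated events could add** (assumed inputs)

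Assume 4 to 8 doses and a constant background of 0.01 to 0.05 unrelated matching events per patient per 30 days. TEAE days = (doses − 1) × 21 + 30, which is 93 days for 4 doses and 177 for 8. P(at least one) = 1 − exp(−rate × days/30).

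- Low end: 1 − exp(−0.01 × 93/30) = 3.1%, or 3 of about 110 treated patients
- High end: 1 − exp(−0.05 × 177/30) = 25.5%, or 28 of 110

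The same formula with 2 days per dose:

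- Low end: 1 − exp(−0.01 × 4 × 2/30) = 0.3%, under 1 patient
- High end: 1 − exp(−0.05 × 8 × 2/30) = 2.6%, about 3 patients

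**Why the net direction is open**

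Assume a true reaction rate of 5%, and let the query catch a fraction s of those patients, independently of background events. The table then shows 1 − (1 − 0.05s) × (1 − p), where p is the share of patients with an unrelated event.

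- s = 1: 1 − 0.95 × 0.969 = 7.9% at the low background, and 1 − 0.95 × 0.745 = 29.3% at the high one. Both overstate.
- Low background, break-even: 1 − 0.05s = 0.95/0.9695 = 0.9799, so s = 0.0201/0.05 = 0.40. If the query catches less than about 40% of true reactions, the table understates.
- High background: the table overstates whatever s is, because p alone exceeds 5%.

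None of these inputs is in the documents.

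**The case against.** The strongest reply is that a broad-plus-narrow query is a deliberately sensitive screen and that the SAP says openly what it counts. The table is descriptive, no test depends on it, and Protocol 8.1.1.3 names no adverse events of special interest. Much of the information also appears elsewhere. Events coded as infusion reactions show up by preferred term in the general TEAE tables. Table 7 requires Grade 3 and 4 reactions to be reported as serious, so they enter the serious TEAE outputs. The all-AE listing gives onset dates. All of this stands and keeps the point minor. It does not answer the heading: timing can be rebuilt patient by patient, but no summary does so.

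Three stronger readings are tempting, and the documents do not support them.

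- A reader might infer that the protocol defines a reaction by a 3-hour limit that the SAP breaks. The phrase "IRR during or within 3 hours after the administration of MIRV" is part of a blood-sampling trigger for Grade 2 or higher events. It differs from the trigger in Section 5.5.5, and the protocol recognises delayed reactions.
- A reader might infer that the table must overstate the rate and shift the grades upward. Without the query's term list, undercounting is also possible, and nothing in the documents shows which way the grade distribution would move.
- A reader might infer that 90% of the table's events are wrong. The figure is a share of cycle time under an assumed even spread. It applies only to unrelated events and says nothing about how many there are.

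**Conclusion.** The concern holds as a mismatch between label and content. Followed exactly, SAP 6.2.2 reports hypersensitivity-type events from the whole TEAE window as infusion-related reactions, with no link to an infusion and without investigator-identified reactions. The output should not be read as an infusion-reaction incidence.

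The size and net direction of the error cannot be computed, because the documents give no background event rate, reaction rate or query term list. The firm arithmetic is the 2/21 (9.5%) share of a cycle; the 90% figure also needs the even-spread assumption. The range of 3.1% to 25.5% of patients rests wholly on the assumed background and number of doses, and shows only that the effect could be trivial or large. The primary analysis is not touched. This is a low-priority correction.

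**What to change.** 1. Retitle the existing table and listing as Hypersensitivity (SMQ), content unchanged.
2. Add an infusion-related-reaction table by preferred term and CTCAE grade. It should contain (a) SMQ-matching TEAEs with onset in a prespecified analysis window, for example the infusion date or the next calendar day, and (b) every adverse event the investigator reports as an infusion reaction, regardless of onset. Show delayed events separately. The window must not be applied to (b), or the delayed reactions that Protocol 5.5.5 recognises would be lost.
3. Reconcile the differing timing phrases in Protocol 5.5.5 and 6.1. The analysis window in step 2 is a reporting convention and does not settle which phrase should govern sampling.

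The cost is a new title, one date filter and one extra descriptive table, built from the infusion administration records and AE onset dates already planned for listing. SAP 1.1 allows changes before final database lock. The downside is that a calendar-day window appears in neither document and still admits a few unrelated events: under 1 to about 3 of 110 patients on the assumptions above.
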